2.2. Study Design

This Phase 3, multicenter, single-arm study will be conducted at investigator sites in the United States.

Approximately 800 children ≥ 15 months to <18 years of age at the time consent (and assent, if applicable) is obtained will be enrolled into 4 cohorts based on age (Cohort 1: ≥ 15 to <24 months, Cohort 2: ≥ 2 to <5 years, Cohort 3: ≥ 5 to <10 years, and Cohort 4: ≥ 10 to <18 years) and will receive a single dose of 20vPnC.

Blood will be collected prior to and 1 month after vaccination for immunogenicity assessments. Participants will be observed for 30 minutes after vaccination and any reactions occurring during that time will be recorded as AEs. Prompted local reactions (redness, swelling, and pain at the injection site), age-applicable systemic events (fever, decreased appetite, drowsiness/increased sleep, and irritability in Cohort 1; and fever, fatigue, headache, muscle pain, and joint pain in Cohorts 2-4), and use of antipyretic/pain medications will be collected via a provided e-diary (or e-diary application) daily for 7 days after vaccination. AEs will be collected from the time informed consent is obtained to 1 month after vaccination. SAEs and NDCMCs will be collected through the 6 months after vaccination.

3. ENDPOINTS AND BASELINE VARIABLES: DEFINITIONS AND CONVENTIONS

The primary, secondary CCI [REDACTED] endpoints pertain to the vaccination with 20vPnC, as described in the objectives. Any reference to participants reporting an event in this SAP should be understood to mean parent(s)/legal guardian(s) or participant, as age appropriate, reporting the event for the participant.

3.1. Primary Endpoint(s)

3.1.1. Primary Safety Endpoint(s)

- Prompted local reactions (redness, swelling, and pain at the injection site) within 7 days of vaccination.
- Prompted systemic events within 7 days of vaccination:
 - **Cohort 1:** Fever, decreased appetite, irritability, and drowsiness/increased sleep
 - **Cohorts 2 through 4:** Fever, fatigue, headache, muscle pain, and joint pain.
- AEs from vaccination to 1 month after vaccination.
- SAEs from vaccination to 6 months after vaccination.

PFIZER GENERAL BUSINESS

- NDCMCs from vaccination to 6 months after vaccination.

3.1.1.1. Local Reactions

The local reactions assessed and reported in the e-diary are redness, swelling, and pain at the injection site, from Day 1 through Day 7, where Day 1 is the day of vaccination. This section describes derivations with details for the assessment of local reactions: presence, severity level, duration, and onset day.

Severity and Maximum Severity

Redness and swelling will be measured and recorded in measuring device (caliper) units (range: 1 to >14; an entry in the e-diary of 15 will denote >14), and then categorized during analysis as mild, moderate, or severe based on the grading scale in Table 3 below.

Measuring device units can be converted to centimeters according to the following scale: 1 measuring device unit = 0.5 cm. Pain at the vaccine injection site will be assessed by the participant as mild, moderate, or severe according to the grading scale in Table 3.

Table 3. Grading Scales for Local Reactions in Study Participants

Local Reaction	GRADE 1 Mild	GRADE 2 Moderate	GRADE 3 ^a Severe	GRADE 4 ^b
Redness	1 to 4 caliper units (or measuring device units) = >0 to 2.0 cm	5 to 14 caliper units (or measuring device units) = >2.0 to 7.0 cm	>14 caliper units (or measuring device units) = >7 cm	Necrosis or exfoliative dermatitis ^b
Swelling	1 to 4 caliper units (or measuring device units) = >0 to 2.0 cm	5 to 14 caliper units (or measuring device units) = >2.0 to 7.0 cm	>14 caliper units (or measuring device units) = >7 cm	Necrosis ^b
Pain at injection site (tenderness)	Cohort 1: Hurts if gently touched (eg, whimpering, winces, protests, or withdraws) Cohorts 2-4: Does not interfere with activity	Cohort 1: Hurts if gently touched with crying Cohorts 2-4: Interferes with activity	Cohort 1: Causes limitation of limb movement Cohorts 2-4: Prevents daily activity ^c	Emergency room visit or hospitalization for severe pain (tenderness) at injection site

Abbreviation: CRF = case report form.

Note: If the size of the redness and/or swelling falls between 2 measuring device units, the higher measuring device unit number will be recorded in the e-diary.

- Parent(s)/legal guardian(s) of the participants experiencing local reactions >14 caliper units (>7.0 cm) are to be contacted by the study site. An unscheduled visit may be required.
- Grade 4 assessment should be made by the investigator. Grade 4 will not be collected in the e-diary but will be collected in the CRF. The severity of the local reaction should be graded using the AE grading scale in Protocol Section 10.3.4.
- Prevents daily activity, eg, results in missed days of work or school or is otherwise incapacitating.

For each local reaction, the maximum severity grade will be derived for the e-diary collection period (Day 1 to Day 7, where Day 1 is the day of vaccination) as follows:

Maximum severity grade = highest grade (maximum severity) within 7 days after vaccination (Day 1 through Day 7) among severity grades reported for that local reaction in the e-diary.

CCI [REDACTED]

[REDACTED]

CCI [REDACTED]

[REDACTED]

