3.1.1.2. Systemic Events (Systemic Event Symptoms and Fever)

The systemic events assessed and recorded in the e-diary for Cohort 1 are fever, decreased appetite, drowsiness/increased sleep, and irritability from Day 1 through Day 7, where Day 1 is the day of vaccination. For Cohorts 2 through 4, the systemic events are fever, fatigue, headache, muscle pain, and joint pain. The derivations for systemic events will be handled similar to the way local reactions are handled: presence, severity level, duration, and onset day. Maximum temperature range over the period from Day 1 through Day 7 will be mapped into the ranges described in [Table 6](#) for summary of maximum temperature.

The systemic events of decreased appetite, irritability, and drowsiness/increased sleep for Cohort 1 and fatigue, headache, muscle pain, and joint pain for Cohorts 2 through 4 will be assessed by the participant's parent(s)/legal guardian(s) as mild, moderate, or severe according to the grading scale in [Table 4](#) or [Table 5](#), respectively. Grade 4 will not be collected in the e-diary but will be collected as an AE on the CRF.

Table 4. Grading Scales for Systemic Events - Participants Who Are ≥ 15 Months to < 2 Years of Age (Cohort 1)

Systemic Event	GRADE 1 Mild	GRADE 2 Moderate	GRADE 3 Severe	GRADE 4 ^a
Decreased appetite (loss of appetite)	Decreased interest in eating	Decreased oral intake	Refusal to feed	Emergency room visit or hospitalization for severe decreased appetite (loss of appetite)
Drowsiness (increased sleep)	Increased or prolonged sleeping bouts	Slightly subdued interfering with daily activity	Disabling not interested in usual daily activity	Emergency room visit or hospitalization for severe drowsiness (increased sleep)
Irritability (fussiness) (synonymous with restless sleep; decreased sleep)	Easily consolable	Requiring increased attention	Inconsolable; crying cannot be comforted	Emergency room visit or hospitalization for severe irritability (fussiness)

Abbreviation: CRF = case report form.

a. Grade 4 assessment should be made by the investigator. Grade 4 will not be collected in the e-diary but will be collected in the CRF. The severity of the systemic event should be graded using the AE severity grading scale.

Table 5. Grading Scales for Systemic Events - Participants Who Are ≥ 2 to < 18 Years of Age (Cohorts 2-4)

Systemic Event	GRADE 1 Mild	GRADE 2 Moderate	GRADE 3 Severe ^a	GRADE 4 ^b

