Fatigue (= tiredness in e-diaries)	Does not interfere with activity	Some interference with activity	Prevents daily routine activity	Emergency room visit or hospitalization for severe fatigue
Headache	Does not interfere with activity	Some interference with activity	Prevents daily routine activity	Emergency room visit or hospitalization for severe headache
Muscle pain	Does not interfere with activity	Some interference with activity	Prevents daily routine activity	Emergency room visit or hospitalization for severe muscle pain
Joint pain	Does not interfere with activity	Some interference with activity	Prevents daily routine activity	Emergency room visit or hospitalization for severe joint pain

Abbreviation: CRF = case report form.

a. Prevents daily routine activity, eg, results in missed days of work or school or is otherwise incapacitating; includes use of narcotics for analgesia.

b. Grade 4 assessment should be made by the investigator. Grade 4 will not be collected in the e-diary but will be collected in the CRF. The severity of the systemic event should be graded using the AE severity grading scale.

[figure not shown]
[figure not shown]
Temperatures recorded in degrees Fahrenheit will be programmatically converted to degrees Celsius first for reporting. Fever will be grouped into ranges for the analysis according to Table 6.

Table 6. Ranges for Fever

≥38.0°C to 38.4°C
>38.4°C to 38.9°C
>38.9°C to 40.0°C
>40.0°C

Note: Fever is defined as a temperature ≥38.0°C.

CCI

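### On the visible text, the primary severity summaries of prompted reactions cannot show Grade 4, because maximum severity is taken from e-diary grades only

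*SAP*

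**What the plan says.** SAP Table 3 grades local reactions on four levels. Redness and swelling are measured by caliper, "and then categorized during analysis as mild, moderate, or severe based on the grading scale in Table 3 below", with "1 measuring device unit = 0.5 cm". Grade 4 is defined differently: necrosis for swelling, necrosis or exfoliative dermatitis for redness, and emergency or inpatient care for severe pain. SAP Tables 4 and 5 define Grade 4 for the systemic symptoms in the same way as for pain. Fever is grouped by temperature range (Table 6) and has no Grade 4.

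Only the investigator can assign Grade 4 (Protocol 8.2.2.1 and 8.2.2.2.1). SAP Section 3.1.1.2 says: "Grade 4 will not be collected in the e-diary but will be collected as an AE on the CRF". The footnotes to the SAP systemic tables likewise say: "Grade 4 will not be collected in the e-diary but will be collected in the CRF". The Table 3 footnote makes the same split for local reactions and adds: "The severity of the local reaction should be graded using the AE grading scale in Protocol Section 10.3.4".

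Maximum severity in SAP 3.1.1.1 is the highest grade on Days 1 to 7 "among severity grades reported for that local reaction in the e-diary". SAP 3.1.1.2 adds: "The derivations for systemic events will be handled similar to the way local reactions are handled". The main analyses in SAP 6.1.1.1.1 and 6.1.1.2.1 report counts, percentages and 95% confidence intervals by maximum severity. Protocol 9.4.2 presents severity cumulatively. SAP Section 4 restricts e-diary summaries to members of the safety population with at least some e-diary data.

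**The concern.** The scale has four grades, but the derivation reads a source that can hold only three. The primary safety objective is descriptive, so the severity tables are themselves the result. A reader who finds nothing above Grade 3 in them could not tell whether no Grade 4 reaction occurred or whether the derivation had no means of showing one.

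Redness and swelling are the most exposed. Their diary grade depends only on diameter, while their Grade 4 is a tissue finding that does not depend on diameter. The two need not agree, and a confirmed Grade 4 reaction could sit in the mild or moderate row.

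**Working it through.** The plan states no figure for this point apart from the unit conversion, so most of the check sets rules side by side.

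**1. Ceiling of the derived grade.** Inputs are the definition of maximum severity (SAP 3.1.1.1) and the Grade 4 footnotes (SAP Tables 3 to 5). Derived maximum = max(diary grade, Days 1 to 7). The diary holds Grades 1, 2 and 3, so the derived maximum is at most 3. The number of participants with derived maximum = 4 is 0 whatever the CRF contains.

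**2. Unit conversion.** 4 units × 0.5 cm = 2.0 cm, the top of Grade 1. 14 units × 0.5 cm = 7.0 cm, the top of Grade 2. Both agree with SAP Table 3.

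**3. Where a confirmed Grade 4 event would appear.** Difference = 4 − diary grade. It counts rows on an ordinal scale and is not an effect size.

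| Event | Largest diary record, Days 1–7 | Shown as | Difference |
|---|---|---|---|
| Redness or swelling | 1–4 units (up to 2.0 cm) | Grade 1 | 4 − 1 = 3 |
| Redness or swelling | 5–14 units (>2.0 to 7.0 cm) | Grade 2 | 4 − 2 = 2 |
| Redness or swelling | >14 units (>7.0 cm) | Grade 3 | 4 − 3 = 1 |
| Pain, systemic symptoms | Severe, if the diary is consistent | Grade 3 | 4 − 3 = 1 |
| Fever | No Grade 4 defined | Unaffected | – |

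The diameter is that of the redness or swelling itself, not of any necrotic area within it.

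**4. No diary entry.** A participant with no e-diary data leaves the e-diary summary altogether (SAP 4). A participant with a diary but no entry for that reaction is not counted as having it. The exact denominator in that case may depend on redacted text.

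**5. Whether another visible output restores the grade.**
- The AE summary (SAP 6.1.1.3.1) is by system organ class and preferred term, with no visible severity split.
- AE intensity stops at severe, the third of three levels (Protocol 10.3.4).
- The unscheduled visit (Protocol 8.10.4) assesses pain by the Section 8.2.2 grades, but measures redness and swelling only by diameter. Other findings go to the AE page.

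No visible primary table shows Grade 4 as such.

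**6. Illustration of scale.** Assume one confirmed Grade 4 reaction in a cohort and e-diary data from all 200 planned participants, with exact Clopper-Pearson limits (SAP 5.2.1).
- Visible rule: Grade 4 = 0/200 = 0%. Upper limit = 1 − 0.025^(1/200) = 1.83%, so the 95% CI is 0 to 1.83%.
- CRF Grade 4 included: 1/200 = 0.5%. Lower limit = 1 − 0.975^(1/200) = 0.01%. Upper limit = 0.975 quantile of Beta(2, 199) = 2.75%.

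Each such event moves an affected row by 1/200 = 0.5 percentage points. The count of one is an assumption, because the documents give no Grade 4 rate.

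**The case against.** The strongest reply is that this is a deliberate design with two data streams. The diary tables summarize what parents report, and Grade 4 events are investigator-confirmed AEs. AEs are a primary safety endpoint in their own right. A confirmed Grade 4 event counts in the AE summary and, if serious, in the SAE summary. The investigator must also notify the sponsor of each one immediately (Protocol 8.2.2.1 and 8.2.2.2.1). For pain and systemic symptoms, Grade 4 presupposes a severe event, so a consistent diary already places it in the severe row. With cumulative presentation, the rows for any severity and for severe are then correct. All of this stands. It limits the point to the severity display but does not let that display show the scale's top grade.

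The second reply is redaction. SAP 3.1.1.1 announces "derivations with details for the assessment of local reactions: presence, severity level, duration, and onset day", yet only severity is visible. Redacted blocks follow the maximum-severity definition and the missing-data statements in SAP 6.1.1.1.1 and 6.1.1.2.1. SAP 5.3 points to missing-data methods in 3.1.1.1 and 3.1.1.2 that cannot be seen. A Grade 4 rule could be there, so a reader should not infer that the plan has none. The visible definition does read as complete, however, and a hidden rule would have to extend or override it.

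A reader might also infer that a small area of necrosis would be shown as mild. The documents do not support that. The diary records the size of the redness or swelling, and a small necrotic centre within redness above 7.0 cm is diary Grade 3. The two lower placements arise only if the redness or swelling itself stays within 2.0 or 7.0 cm on every diary day. The documents do not say how often that happens.

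**Conclusion.** The point holds as a minor one. On the visible text, the primary severity summaries of local reactions and systemic symptoms cannot show Grade 4. A confirmed case appears at its diary grade or is absent from those summaries. For redness and swelling this could be Grade 1, 2 or 3. For pain and systemic symptoms with a consistent diary, only the distinction from other severe events is lost. Fever is unaffected.

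The conclusion rests on two assumptions: that no redacted text adds CRF Grade 4 events to the derivation, and that systemic symptoms follow the local-reaction definition, which the SAP says only by analogy. No frequency can be given.

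A reader might conclude that serious reactions disappear from the safety results. They do not: the event remains in the AE summary and, if serious, in the SAE summary. The immunogenicity hypothesis tests do not use these data.

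**What to change.** Check whether the redacted parts of SAP 3.1.1.1, 3.1.1.2, 6.1.1.1 and 6.1.1.2 already handle Grade 4. If they do not, state the following in the SAP before database lock:

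- Maximum severity is the highest Day 1 to 7 grade across the e-diary and any investigator-confirmed Grade 4 prompted event in the CRF.
- Grade 4 has its own row in the local-reaction and systemic-symptom summaries, but not for fever.
- A confirmed Grade 4 case in a participant with no e-diary data is reported in a footnote.

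Also confirm that the CRF keeps the Grade 4 classification beside the three-level AE intensity, and add a flag only if it does not.

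The cost is a few SAP sentences and one data merge. The cases are already known to the sponsor through the notification rule. The downside is that a safety figure may look slightly less favourable.

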3.1.1.2. Systemic Events (Systemic Event Symptoms and Fever)

The systemic events assessed and recorded in the e-diary for Cohort 1 are fever, decreased appetite, drowsiness/increased sleep, and irritability from Day 1 through Day 7, where Day 1 is the day of vaccination. For Cohorts 2 through 4, the systemic events are fever, fatigue, headache, muscle pain, and joint pain. The derivations for systemic events will be handled similar to the way local reactions are handled: presence, severity level, duration, and onset day. Maximum temperature range over the period from Day 1 through Day 7 will be mapped into the ranges described in [Table 6](#) for summary of maximum temperature.

The systemic events of decreased appetite, irritability, and drowsiness/increased sleep for Cohort 1 and fatigue, headache, muscle pain, and joint pain for Cohorts 2 through 4 will be assessed by the participant's parent(s)/legal guardian(s) as mild, moderate, or severe according to the grading scale in [Table 4](#) or [Table 5](#), respectively. Grade 4 will not be collected in the e-diary but will be collected as an AE on the CRF.

Table 4. Grading Scales for Systemic Events - Participants Who Are ≥ 15 Months to < 2 Years of Age (Cohort 1)

Systemic Event	GRADE 1 Mild	GRADE 2 Moderate	GRADE 3 Severe	GRADE 4 ^a
Decreased appetite (loss of appetite)	Decreased interest in eating	Decreased oral intake	Refusal to feed	Emergency room visit or hospitalization for severe decreased appetite (loss of appetite)
Drowsiness (increased sleep)	Increased or prolonged sleeping bouts	Slightly subdued interfering with daily activity	Disabling not interested in usual daily activity	Emergency room visit or hospitalization for severe drowsiness (increased sleep)
Irritability (fussiness) (synonymous with restless sleep; decreased sleep)	Easily consolable	Requiring increased attention	Inconsolable; crying cannot be comforted	Emergency room visit or hospitalization for severe irritability (fussiness)

Abbreviation: CRF = case report form.

a. Grade 4 assessment should be made by the investigator. Grade 4 will not be collected in the e-diary but will be collected in the CRF. The severity of the systemic event should be graded using the AE severity grading scale.

Table 5. Grading Scales for Systemic Events - Participants Who Are ≥ 2 to < 18 Years of Age (Cohorts 2-4)

Systemic Event	GRADE 1 Mild	GRADE 2 Moderate	GRADE 3 Severe ^a	GRADE 4 ^b
Fatigue (= tiredness in e-diaries)	Does not interfere with activity	Some interference with activity	Prevents daily routine activity	Emergency room visit or hospitalization for severe fatigue
Headache	Does not interfere with activity	Some interference with activity	Prevents daily routine activity	Emergency room visit or hospitalization for severe headache
Muscle pain	Does not interfere with activity	Some interference with activity	Prevents daily routine activity	Emergency room visit or hospitalization for severe muscle pain
Joint pain	Does not interfere with activity	Some interference with activity	Prevents daily routine activity	Emergency room visit or hospitalization for severe joint pain

Abbreviation: CRF = case report form.

a. Prevents daily routine activity, eg, results in missed days of work or school or is otherwise incapacitating; includes use of narcotics for analgesia.

b. Grade 4 assessment should be made by the investigator. Grade 4 will not be collected in the e-diary but will be collected in the CRF. The severity of the systemic event should be graded using the AE severity grading scale.

[figure not shown]
[figure not shown]
Temperatures recorded in degrees Fahrenheit will be programmatically converted to degrees Celsius first for reporting. Fever will be grouped into ranges for the analysis according to Table 6.

Table 6. Ranges for Fever

≥38.0°C to 38.4°C
>38.4°C to 38.9°C
>38.9°C to 40.0°C
>40.0°C

Note: Fever is defined as a temperature ≥38.0°C.

CCI

3.1.1.4. Adverse Events

[figure not shown]
AEs will be categorized according to MedDRA terms. AEs will be assessed from the time of informed consent through 1 month after vaccination.

AE reporting will be based on the specific reporting period. Missing AE start dates will be imputed following the Pfizer data standard rules as described in [Section 5.3](#).

3.1.1.5. Serious Adverse Events and Newly Diagnosed Chronic Medical Conditions

SAEs and NDCMCs will be categorized according to MedDRA terms. SAEs and NDCMCs will be collected from the signing of informed consent through the end of the study.

PFIZER GENERAL BUSINESS

3.1.2. Primary Immunogenicity Endpoint(s)

- Cohorts 1 and 2: Pneumococcal serotype-specific IgG concentrations for the 7 additional serotypes (8, 10A, 11A, 12F, 15B, 22F, and 33F) before and 1 month after 20vPnC
- Cohorts 3 and 4: Pneumococcal serotype-specific OPA titers for the 7 additional serotypes before and 1 month after 20vPnC

Concentrations of anticapsular IgG and OPA titers for each pneumococcal serotype will be determined for each participant using the Luminex assay and Pfizer's OPA assay, respectively, both before vaccination and 1 month after vaccination.

Fold changes will be calculated for each participant by taking the ratio of assay results from the later visit to the earlier visit.

3.2. Secondary Endpoint(s)

- Pneumococcal serotype-specific IgG concentrations before and 1 month after 20vPnC

To support the secondary pneumococcal immunogenicity estimands, IgG concentrations will be classified based on serotype-specific IgG reference concentrations as defined below in Table 7 for the 7 additional serotypes in Cohort 1.

Table 7. Predefined Pneumococcal Serotype-Specific IgG Concentrations

Serotypes	Reference Concentration ($\mu\text{g/mL}$)
1, 3, 4, 6A, 7F, 9V, 14, 18C, 19F, 23F	≥ 0.35
5	≥ 0.23
6B	≥ 0.10
19A	≥ 0.12
8, 10A, 11A, 12F, 15B, 22F, 33F	≥ 0.35 [REDACTED]
CCI	[REDACTED]

Abbreviation: TBD = to be determined.

C
C
I

[figure not shown]
PFIZER GENERAL BUSINESS

Fold changes in IgG concentrations will be calculated for each participant by taking the ratio of assay results from the later visit to the earlier visit for the 13vPnC serotypes in Cohorts 1 and 2 and for all 20 serotypes in Cohorts 3 and 4.

- Pneumococcal serotype-specific OPA titers before and 1 month after 20vPnC
 - Fold changes in OPA titers for all 20 serotypes in Cohorts 1 and 2 and for the 13vPnC serotypes in Cohorts 3 and 4 (see [Section 3.1.2](#) for calculations)
 - Classification of fold changes as a ≥ 4 -fold rise for the 7 additional serotypes in Cohorts 2, 3, and 4. The 4-fold rise in OPA titers is being performed on children traditionally considered to have a more mature immune response to polysaccharide antigens (≥ 2 years of age)¹

OPA titers will be determined on serum from randomly selected subsets of participants provided by the study statistician, with the exception of the 7 additional serotypes in Cohorts 3 and 4, which will be assayed for all subjects in those cohorts. Further details of the subsetting will be described in a memo.

CCI

C
C
I
I

